## 1.0 Research Design

## 1.1 Purpose/Specific Aims

To examine clinical relevance and test for a causative role of gut microbiota in the context of appetite regulation and food-related behavior in patients with hyperphagia syndrome

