## A. Objectives

To use high-fiber supplementation, an intervention known to create shifts in the gut microbiota towards a healthier structure, to explore the relationship between gut microbiota, appetite control and feeding behavior in patients with hyperphagia syndrome.

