TESTING AND INTERVENTION. Participants will attend a baseline visit at the Center for Advanced Human Brain Imaging Research (CAHBIR) at Rutgers University, during which functional magnetic resonance imaging (fMRI) coupled with a meal test will be performed to assess peripheral and central feeding pathways (7, 8). fMRI scans will be performed during resting state to assess functional connectivity of feeding related networks, with a specific focus on connectivity between the hypothalamus, insula, anterior cingulate, ventromedial/orbitofrontal prefrontal cortex and amygdala (9, 10). Activation to food (vs non-food) images will be assessed to index responsivity to appetitive feeding networks including the above regions and the ventral striatum using paradigms that have previously been found to be sensitive to trait and state in multiple studies (11-13). Thereafter participants will consume a liquid meal (525 kcal; Ensure Plus, Abbott). fMRI will be repeated immediately after the meal. Participants will attend a second visit at the IFNH, during which laboratory work coupled with a meal test will be performed to assess satiety hormones and inflammatory markers. Fasting blood draw will be taken, and the participants will consume a liquid meal (525 kcal; Ensure Plus, Abbot) followed by blood draws at 30, 60, 120, 180 and 240 min postmeal. Upon completion of baseline testing and providing a fecal sample, participants will consume NBT-NM108 (a mixture of inulin, Fibersol-2, and brans of oat, wheat, corn and sorghum; Notitia Biotechnologies) daily for 4 weeks. At the completion of the 4-week intervention, all sampling and testing will be repeated as per baseline. At baseline and end of intervention, participants will be interviewed with appetite and physical activity questionnaires (Appendix C and G) and requested to complete a 24-h food recall using MyFitnessPal, a mobile health app on their phone.

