## 1.5 Sample Size Justification

No power calculation is performed for this pilot study. We aim to recruit 10 patients with hyperphagia(5 male and 5 female) to capture a reasonable degree of variations in gut microbiota composition.

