## 4.3 Number of Subjects

A. Total Number of Subjects

10 patients; 5 male and 5 female

- B. Total Number of Subjects If Multicenter Study N/A
- C. Feasibility

DEEP6 identified 26 patients via EPIC system who had the diagnosis of PWS with only 5 patients meeting our inclusion criteria. For this reason we are expanding our diagnosis coding to include hyperphagia syndrome. Given hyperphagia is a hallmark feature of PWS and the particular behavior we are aiming to study, this expansion should improve our subject pool and allow us to enroll 10 patients.

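### The aim in section 1.1 promises a test of whether gut microbiota cause appetite change, but a single-group before-after study with no comparator can support only change over time and association

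*Combined protocol and SAP*

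**What the plan says.** All references are to the combined protocol and SAP.

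- **Aim (section 1.1).** The aim has two parts: "To examine clinical relevance and test for a causative role of gut microbiota in the context of appetite regulation and food-related behavior". The second part, to "test for a causative role of gut microbiota", is the one at issue.
- **Objective (section 1.1 A).** The wording is weaker. Fibre supplementation is to be used "to explore the relationship between gut microbiota, appetite control and feeding behavior in patients with hyperphagia syndrome".
- **Intervention (section 1.3 A, Testing and Intervention).** After baseline testing, "participants will consume NBT-NM108 (a mixture of inulin, Fibersol-2, and brans of oat, wheat, corn and sorghum; Notitia Biotechnologies) daily for 4 weeks". Then: "At the completion of the 4-week intervention, all sampling and testing will be repeated as per baseline".
- **Size (sections 1.5 and 4.3).** Section 4.3 gives "10 patients; 5 male and 5 female". Section 1.5 says "No power calculation is performed for this pilot study".
- **Predictor (section 1.6 A).** NBT-NM108 is the only entry, with no comparison level.
- **Analysis (section 6.1).** Week 0 is compared with week 4, and males with females. MaAsLin2 and similar models relate sequence variants, co-abundance groups and predicted functions to the clinical data. The extracted fMRI measures follow similar procedures.

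**The concern.** A test of causation needs a contrast that isolates the supposed cause. The aim names gut microbiota as the cause and appetite and food-related behavior as the effect, so two links have to be established: that the product changed the outcome, and that it did so through the microbiota. The plan appears to contain no contrast for either. The aim also asks for more than the objective directly below it.

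What is at stake is the interpretation of the results. If 1.1 stands, a week 4 change or an association between microbes and appetite can be read against an aim that calls the study a causal test, although the design gives it no such standing. The consent procedure in section 1.3 A has the coordinator explain the aim to candidates, so the wording also affects how the study is described to participants and their surrogates.

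**Working it through.** The plan gives no figure to reproduce here, so the check sets the sections side by side.

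1. **Is there a comparator?** Sections 1.3 A, 1.6 A and 4.3 describe one group in which everyone takes the product. No placebo, untreated group, randomization, crossover, run-in or second baseline appears. Weight is also taken at weeks 1, 2 and 3 (section 1.3 D), but those points fall within treatment. The only between-group contrast in 6.1 is male against female.

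2. **Link one, product to outcome.** The week 0 to week 4 difference is the sum of any product effect and any change that would have happened anyway. With one group and one baseline, only the sum can be estimated. Plausible contributors to the second term are time and repeat testing. Expectation is another, because participants know what they are taking and are told the expected outcomes at consent. It bears mainly on appetite, collected by interview questionnaire, and intake, taken from a 24-hour recall. It bears much less on stool sequencing, the primary outcome.

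3. **Link two, microbiota to outcome.** The fibre is the only thing manipulated, and it changes the diet and the microbiota together. Section 4.7 A says the product is low in digestible carbohydrate and may lower intake, without attributing that to the microbiota. No part of the design holds one route fixed while the other varies. Section 6.1 names association models and no mediation or other causal analysis.

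4. **Comparison with the plan's own evidence.** Section 1.4 describes transplantation of patients' microbiota into germ-free mice and treats that as evidence of causality, for metabolic traits and not appetite. It also describes a randomized comparison with usual care in type 2 diabetes. This trial has neither feature.

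5. **Would a control arm within the same 10 people rescue the aim?** Assume a two-sided 5% level (the plan states none) and 5 per arm. A two-sample t-test has 8 degrees of freedom and noncentrality d × √(5/2), where d is the difference in SD units. Power of 80% requires d of about 2.02 (2.02 × 1.58 = 3.2). So only a difference of about 2 SD would be detectable with that power, and the contrast would still test the product, not the microbiota.

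**The case against.** The strongest reply is that this is half of one sentence in a pilot that is otherwise modest. The objective says explore, section 1.5 calls the study a pilot, and section 6.1 speaks of testing differences and interpreting relationships. Nowhere do the documents say that a change will be attributed to the product or published as causal; section 6.4 C says only that findings will be presented and published. Before-after designs can also support causal conclusions when the untreated course is known to be stable.

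Much of this stands and limits the point to the wording. The last argument does not help here: there is a single baseline and no run-in, and the protocol makes no case for a stable untreated course.

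A reader might also infer several stronger things that the documents do not support:

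- **That 10 patients is why causation cannot be tested.** Sample size limits precision. More patients in the same design would estimate the same mixture more precisely and leave the bias in place.
- **That a false-positive rate can be attached.** Any such rate needs an assumed size of non-specific shift and an assumed significance level; the plan gives neither. A rate for the paired t-test would not describe the primary outcome either, because differences in microbiota structure are tested by PERMANOVA.
- **That regression to the mean is a leading bias.** Entry is by genetic diagnosis or diagnostic coding (section 4.1 B), not by an extreme score on an outcome. The one limit on an outcome is the 300 lb weight cap, which would tend to push mean weight up on retest and so would not mimic benefit.
- **That the whole aim fails.** The clinical-relevance half does not depend on a causal contrast.

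**Conclusion.** The point holds for the causal wording in section 1.1. As designed, the trial can estimate 4-week change during NBT-NM108 and describe associations. It cannot test whether gut microbiota cause changes in appetite or food-related behavior, because there is no comparator and the microbiota is not manipulated apart from the fibre. The size is a matter of kind, not degree: the causal half of the aim is out of reach at any sample size under this design, while the clinical-relevance half and the objective in 1.1 A remain open to descriptive answers.

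This rests on reading the design as single-group and uncontrolled. The documents do not use those terms, but sections 1.3 A, 1.6 A, 4.3 and 6.1 all point that way and none contradicts it. It does not rest on any assumed effect size, or on any prediction of how the authors will report.

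**What to change.** Three wording changes:

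1. **Section 1.1.** Remove the causal clause and match the objective, for example: *To examine the clinical relevance of gut microbiota to appetite and feeding in hyperphagia; to estimate the 4-week change in gut microbiota composition and in the listed secondary outcomes (weight, hormones, inflammatory markers, fMRI, caloric intake, appetite, physical activity) during NBT-NM108; and to explore their association.*
2. **Section 1.1 B.** Mark the mechanistic hypothesis, that dysbiosis alters central appetite signaling, as one this study does not test causally. Otherwise the causal claim survives there.
3. **Section 6.1.** State that week 0 against week 4 results and MaAsLin2 results will be interpreted and reported as uncontrolled change and association.

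The cost is protocol text only, with no change to procedures, sample size or tests. The downside is that the trial claims less. An extra stool sample a few days before treatment would not substitute for the rewording: a few untreated days cannot serve as a control for a 4-week change, and they would not separate the fibre from the microbiota.

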## A. Objectives

To use high-fiber supplementation, an intervention known to create shifts in the gut microbiota towards a healthier structure, to explore the relationship between gut microbiota, appetite control and feeding behavior in patients with hyperphagia syndrome.

## B. Hypotheses / Research Question(s)

We hypothesize that the gut microbiota in patients with hyperphagia is deficient in carbohydrate-utilizing short-chain fatty acid (SCFA) producers and dominated by bacteria that produce detrimental compounds. Such dysbiosis produces distinct profiles of bioactive compounds, including the proinflammatory lipopolysaccharide (LPS), that contribute to altered signaling in central appetite regulation.

## **1.2 Research Significance**

Hyperphagia is a hallmark feature in PWS patients, with obsessive preoccupation with food and extreme overeating (energy intake of PWS patients may be 3-6 times that of controls (1, 2)) leading to obesity and the related co-morbidities that become one of the leading causes of death in this patient population (3). There is some evidence for hypothalamic dysfunction as an underlying mechanism for PWS-associated hyperphagia (4) but there is no effective treatment to normalize food-related behaviors. The emerging literature on the role of gut microbiota in the gut-brain axis may provide a novel perspective of feeding dysregulation associated with PWS and facilitate novel therapeutic approaches. In our previous study, highfiber intervention induced significant shifts in the gut microbiota structure in PWS patients, an effect associated with improvements in metabolic parameters including body weight and glucose homeostasis and a modest improvement in the overall food-related behavior (5). Data from animal studies further support a plausible mechanism by which gut microbiota participates in the gut-brain axis to regulate food-related behavior (6): SCFAs generated from bacterial fermentation signal entergendocrine cells for the production of appetite-regulating hormones including glucagon-like peptide-1 and peptide YY; LPS from Gramnegative bacteria disrupt the blood-brain barrier and thus enhances the effect of circulating cytokines on central feeding pathways. Other mechanisms that gut microbiota may regulate appetite include the production of neurotransmitters and neuromodulators (e.g., y-amino butyric acid from Bifidobacterium and serotonin from Enterococcus spp.) that act on afferent axons locally or interact with the intestinal cells to modify neural signaling to the central nervous system.

## **1.3 Research Design and Methods**

## A. Research Procedures

**RECRUITMENT.** We are recruiting patients with hyperphagia aged 18-45 years who have not received growth hormone treatment in the previous 6 months. Study candidates will be recruited from Robert Wood Johnson Medical School (RWJMS) pediatric endocrine clinic as well as DEEP6, which applies artificial intelligence to identify patients meeting study criteria in the RWJMS outpatient electronic medical record.

## ELIGIBILITY SCREENING.

For recruitment, individuals with patients with hyperphagia will be identified via [name] RWJMS clinic and DEEP6. Patients identified on the DEEP6 list will be considered for the study if they are patients of [name]. Once identified, the research staff in Rutgers will contact the patient and guardian via a phone call to provide an overview of the study, requirements for research participation, and review eligibility for the study (**Appendix A**). The study candidates and guardians will be informed whether they may be eligible for the study, and if so, a virtual informed consent

HRP-503a - TEMPLATE - Interventional Research Protocol 1.1.21 Protocol Title: Gut microbiota and hyperphagia in PWS Protocol Version Date: October 7, 2022

interview with the research team will be scheduled **(Appendix B).** Female candidates will be given two pregnancy test kits (Rapid Detection Pregnancy Test, Clearblue, Geneva, Switzerland) via mail and will perform the test on the day of the fMRI.

**INFORMED CONSENT AND ELIGIBILITY SCREENING PART 2.** The informed consent process will be conducted virtually through Rutgers Zoom, which is HIPPA protected. The study coordinator will explain the rationale, aim, expected outcomes significance of the research, the experimental procedures, what is required from the participants, and the benefits and risks associated with the study. Informed consent form and consent for health information release will be signed during the interview using DocuSign, a HIPPA compliant platform during the interview (**Appendix B**). The study candidates will receive copies of both signed documents. Upon completing these documents, the study coordinator will ask some additional questions regarding their medical history and other conditions to establish eligibility. Candidates will perform and present proof of a negative pregnancy test result the first study session.

TESTING AND INTERVENTION. Participants will attend a baseline visit at the Center for Advanced Human Brain Imaging Research (CAHBIR) at Rutgers University, during which functional magnetic resonance imaging (fMRI) coupled with a meal test will be performed to assess peripheral and central feeding pathways (7, 8). fMRI scans will be performed during resting state to assess functional connectivity of feeding related networks, with a specific focus on connectivity between the hypothalamus, insula, anterior cingulate, ventromedial/orbitofrontal prefrontal cortex and amygdala (9, 10). Activation to food (vs non-food) images will be assessed to index responsivity to appetitive feeding networks including the above regions and the ventral striatum using paradigms that have previously been found to be sensitive to trait and state in multiple studies (11-13). Thereafter participants will consume a liquid meal (525 kcal; Ensure Plus, Abbott). fMRI will be repeated immediately after the meal. Participants will attend a second visit at the IFNH, during which laboratory work coupled with a meal test will be performed to assess satiety hormones and inflammatory markers. Fasting blood draw will be taken, and the participants will consume a liquid meal (525 kcal; Ensure Plus, Abbot) followed by blood draws at 30, 60, 120, 180 and 240 min postmeal. Upon completion of baseline testing and providing a fecal sample, participants will consume NBT-NM108 (a mixture of inulin, Fibersol-2, and brans of oat, wheat, corn and sorghum; Notitia Biotechnologies) daily for 4 weeks. At the completion of the 4-week intervention, all sampling and testing will be repeated as per baseline. At baseline and end of intervention, participants will be interviewed with appetite and physical activity questionnaires (Appendix C and G) and requested to complete a 24-h food recall using MyFitnessPal, a mobile health app on their phone.

## B. Data Points

- Gut microbiota composition: fecal samples will be collected at weeks 0 and 4.
- fMRI scans will be completed at baseline and end of intervention.
- Blood parameters (satiety hormones and inflammatory markers) at minutes 0, 30, 60, 120, 180, and 240 post-meal at week 0 and week 4.
- Appetite and physical activity questionnaires at weeks 0 and 4.
- Calorie count calculated via 24-h food recall on MyFitnessPal at weeks 0 and 4.

## C. Study Duration

It will take each participant 28 days to complete the study. The overall duration of the study is one year.

## D. Endpoints

[figure not shown]
- 1. Primary Outcome
  - Gut microbiota composition at Weeks 0 and 4
- 2. Secondary outcomes:

- Weeks 0, 1, 2, 3, and 4
  - a. Weight measured in pounds
- Weeks 0 and 4
  - a. Hormones related to satiety and hunger include ghrelin, peptide YY (PYY), leptin, glp-1/GIP, insulin, glucose
  - b. Inflammatory markers include c-reactive protein (CRP), interleukin 6 (IL-6) and tumor necrosis factor-alpha (TNF-), adiponectin
  - c. Outcome of fMRI showing responsivity of appetite feeding networks in the brain
  - d. Caloric intake recorded in MyFitnessPal application
  - e. Appetite behavior measured by hyperphagia questionnaire and visual analog scale (VAS)
  - f. Physical activity measured by physical activity questionnaire

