## 6.0 Data Management Plan

## 6.1 Data Analysis

Microbiome sequencing data will be analyzed based on the amplicon sequence variants (ASVs) [28] to determine the gut microbiota composition using QIIME 2 [29]. Shannon index and ASV richness will be used to assess alpha diversity. Principal coordinate analysis will be used to compare and visualize dissimilarity in gut microbiota structure between samples based on beta diversity (Weighted and Unweighted UniFrac distance) and statistical differences will be tested using permutational multivariate analysis of variance (PERMANOVA). PICRUSt 2 will be used to predict the functions of individual ASVs and the collective functions of the gut microbiota at the gene content and pathway levels [30]. Global functional profiles of the gut microbiota will be compared and visualized by principal component analysis. Repeat measures correlation will be used to assess the relationships between ASVs [31], followed by ASV clustering based on co-abundance patterns. Multivariate methods such as MaAsLin2, that allow adjustment for confounding variables and model the covariates as random effects, will be applied to interpret the relationship between ASVs / ASV co-abundance groups / functions and the clinical metadata.

Difference in continuous variables of metadata, such as measurements of hormones, blood inflammatory markers and total caloric intake, between week 0 and week 4 will be tested by Paired t-test (two-tailed) if meeting normal distribution or Paired Wilcoxon Signed-Rank test (two-tailed) if not meeting normal distribution. Difference in the continuous variables of metadata between male and female will be tested by Student's t-test (two-tailed) if meeting normal distribution or Mann-Whitney test if not meeting normal distribution. Fisher's exact test will be used to compare proportions of categorical metadata, such as data in the appetite and physical activity questionnaires, between male and female, and between Week 0 and Week 4. The false discovery rate will be applied for multiple testing, where appropriate.

HRP-503a - TEMPLATE - Interventional Research Protocol 1.1.21 Protocol Title: Gut microbiota and hyperphagia in PWS Protocol Version Date: October 7, 2022

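### The primary outcome, gut microbiota composition, has no named primary metric or test, the false discovery rate sentence does not say whether it covers the candidates, and PERMANOVA is not stated to be paired

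*Combined protocol and SAP*

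**What the plan says.** Section 1.3 D states the primary outcome in full as "Gut microbiota composition at Weeks 0 and 4". It gives no metric, contrast, test or rule for a positive result.

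Section 6.1 supplies the metrics without ranking them:

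- **Alpha diversity.** "Shannon index and ASV richness will be used to assess alpha diversity". No test is attached.
- **Beta diversity.** Weighted and unweighted UniFrac distances are compared between samples, and "statistical differences will be tested using permutational multivariate analysis of variance (PERMANOVA". Week 0 against week 4 is not named as the contrast, and neither pairing nor restricted permutation is mentioned.
- **Predicted functions, ASVs and co-abundance groups.** Functional profiles are compared by principal component analysis, with no test named. Multivariate models such as MaAsLin2 "will be applied to interpret the relationship between ASVs / ASV co-abundance groups / functions and the clinical metadata".

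For continuous clinical variables the same section does specify a paired comparison of weeks 0 and 4, which "will be tested by Paired t-test (two-tailed) if meeting normal distribution or Paired Wilcoxon Signed-Rank test (two-tailed) if not meeting normal distribution". The paragraph on these variables ends: "The false discovery rate will be applied for multiple testing, where appropriate". No family, level or procedure is given. No significance level appears anywhere in the document.

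Section 1.5 sets the sample at 10 patients, without a power calculation.

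**The concern.** Two analysts could follow section 6.1 exactly and report different primary results. One could lead with Shannon index, the other with unweighted UniFrac, and each could decide after seeing all the results. A reader of the publication could not tell whether the leading metric was chosen in advance.

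The silence on pairing matters separately. Each participant supplies a stool sample at week 0 and another at week 4. The plan respects this pairing for hormones and caloric intake, but does not say so for the only test attached to the primary outcome. If labels were permuted freely across all samples, differences between people would swamp the change within people, and a real shift could be missed. An analyst could then be drawn towards whichever other metric gave a result.

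**Working it through.** The plan states no significance level, power or error rate, so it has no figure of its own to reproduce.

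**Inputs from the plan.** Four candidate metrics, two with a named test (6.1); 10 participants in one group, with stool at weeks 0 and 4 (1.3 B, 1.5).

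**Assumptions.** A 5% level per test, no adjustment and no true change. Shannon index and ASV richness are tested with the paired tests that 6.1 gives for clinical variables; the plan does not say this. The correlations and simulated communities are also assumed.

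**Step 1: independent tests.** The chance of at least one false positive among k tests is 1 − (1 − 0.05)^k.

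- Two UniFrac tests: 1 − 0.95² = 1 − 0.9025 = 9.75%.
- All four metrics: 1 − 0.95⁴ = 1 − 0.8145 = 18.5%.

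Positive correlation lowers these figures. Under any dependence at all, the ceilings are 2 × 5% = 10% and 4 × 5% = 20%.

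**Step 2: correlated tests.** Four equally correlated paired t-tests were simulated with 10 pairs and 40,000 runs per row. The last two columns show what adjustment across all four would achieve.

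| Correlation | Any of four, unadjusted | Bonferroni (1.25% each) | Benjamini-Hochberg at 5% |
|---|---|---|---|
| 0 | 18.6% | 4.9% | 5.0% |
| 0.3 | 17.9% | 4.8% | 5.0% |
| 0.5 | 16.1% | 4.4% | 4.7% |
| 0.7 | 13.7% | 4.0% | 4.4% |
| 0.9 | 10.0% | 2.9% | 3.7% |
| 0.99 | 6.6% | 1.8% | 4.0% |

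With normal instead of t statistics, the unadjusted figures at 0.5, 0.7 and 0.9 are 15.7%, 12.9% and 9.4%. Together these give about 9% to 16% for correlations of 0.9 to 0.5. For two tests only, the t simulation gives 9.4% at 0.5 and 7.4% at 0.9.

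**Step 3: pairing, with no true change.** Communities for 10 participants at two visits were simulated, 600 runs per setting. Bray-Curtis and Jaccard distances stood in for weighted and unweighted UniFrac.

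| SD between / within participants | Permutation | PERMANOVA rejects (two distances) | Any of four metrics |
|---|---|---|---|
| 1.5 / 0.7 | unrestricted | 0.0%, 0.0% | 7.3% |
| 1.5 / 0.7 | within participant | 4.3%, 3.2% | 13.5% |
| 1.0 / 1.0 | unrestricted | 0.2%, 0.0% | 7.2% |
| 1.0 / 1.0 | within participant | 5.5%, 4.7% | 15.3% |
| 0 / 1.0 | unrestricted | 3.8%, 5.2% | 13.3% |
| 0 / 1.0 | within participant | 4.0%, 4.8% | 13.5% |

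When participants differ from one another, unrestricted PERMANOVA almost never rejects. In those rows nearly all of the remaining 7% comes from the two alpha-diversity tests.

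**Step 4: pairing, with a real shift.** In a separate simulation of 10 pairs (assumed communities, Bray-Curtis as stand-in), unrestricted permutation rejected in 0% of runs without a shift and in 0% to 7% of runs with one. Within-participant permutation rejected in 6% and in 12% to 89% respectively.

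**The case against.** The strongest reply has four parts.

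1. **Only two metrics have a named test.** A reader might infer that the plan tests four metrics and so carries an 18.5% error rate. The text does not support that. Shannon index and richness are only said to assess alpha diversity, and the paired tests are assigned to clinical variables. The documented multiplicity is two tests. Nor do the functional and ASV-level analyses clearly add to it: no test is named for the functional profiles, and the MaAsLin2 models address relations with clinical data, not change from week 0 to week 4. This stands, and 18.5% is therefore conditional.
2. **A multiplicity provision exists.** A reader might infer that there is no error control. That is also unsupported. The false discovery rate sentence is not expressly limited to clinical variables, and Benjamini-Hochberg across all four metrics would hold the chance of any false positive at or below about 5% when nothing has changed. What remains is that the sentence leaves its use to judgement and does not commit to these metrics.
3. **The figures rest on assumptions.** No level is stated, and metrics from the same samples are probably correlated. If PERMANOVA ignored pairing, the any-of-four figure would be about 7% where participants differ. This stands. However, that lower figure comes from a test with almost no ability to detect a shift, which is no reassurance.
4. **This is a small exploratory pilot.** The objective in 1.1 A is exploratory and no power calculation was made, so a confirmatory error rate is not the right yardstick. This largely stands, and it makes selective reporting the main issue. It does not remove the need to define an outcome that the protocol itself calls primary, in a trial whose purpose (1.1) includes testing a causative role and whose findings are to be published (6.4 C).

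**Conclusion.** The point holds as a gap in definition. No primary metric or test is named, four unranked candidates are listed, the scope of the false discovery rate sentence is open, and pairing is unstated for the one test attached to the primary outcome.

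At an assumed 5% per unadjusted test, with tests independent or positively correlated, the false-positive chance is up to 9.75% for the two UniFrac tests and up to 18.5% if all four metrics are tested. These are limits under stated assumptions, not the plan's actual error rate. It would be wrong to conclude that the plan fixes an error rate well above 5%: with the false discovery rate applied across all four metrics it would be about 5% or less.

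The pairing question has the opposite effect. In the simulations, unrestricted permutation left PERMANOVA very conservative and largely unable to see a real shift. The direction follows from differences between participants; the exact percentages depend on the assumed communities and the stand-in distances.

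**What to change.** In 1.3 D and 6.1, name one primary test. For example: the week 0 against week 4 difference in weighted UniFrac distance, by PERMANOVA with permutations restricted within participant, at a 5% level. The level needs no two-sided label, because pseudo-F is an upper-tail statistic. Weighted UniFrac suits the hypothesis in 1.1 B, which concerns which bacteria dominate, but it is not the only defensible choice. What matters is that the choice is made before the data are seen.

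Then state that:

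- unweighted UniFrac, Shannon index and ASV richness are supportive, all are reported, and false discovery rate control applies across the three;
- Shannon index and ASV richness are compared between weeks 0 and 4 by a named paired test;
- the functional and ASV-level analyses are exploratory.

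If the sponsor prefers not to choose one metric, the plan should state that false discovery rate or Bonferroni control covers all four.

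The restricted test is workable at this size. Ten complete pairs give 2¹⁰ = 1,024 within-participant labelings. Swapping every label leaves pseudo-F unchanged, so the smallest attainable p-value is 2/1,024 = 0.002. With six complete pairs it is 2/64 = 0.031; with five it is 2/32 = 0.0625, and a 5% result would be out of reach.

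The cost is a few sentences and no new data. The downside is that a change seen only in a supportive metric could not be called the primary result.
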